### **Study Arms and Duration**

The study will consist of 5 treatments. Each enrolled participant will participate in 4 study periods to receive 4 different treatments according to the sequence determined by randomization:

- Treatment A: Single oral dose of nirmatrelvir/ritonavir 300 (2 × 150)/100 mg commercial tablets under fasted conditions (Reference)
- Treatment B: Single oral dose of nirmatrelvir/ritonavir 300/100 mg (2 × 150/50 mg) FDC tablets Test formulation 1 (low disintegrant) under fasted conditions (Test 1)

- Treatment C: Single oral dose of nirmatrelvir/ritonavir 300/100 mg (2 × 150/50 mg) FDC tablets Test formulation 2 (high disintegrant) under fasted conditions (Test 2)
- Treatment D: Single oral dose of nirmatrelvir/ritonavir 300/100 mg (2 × 150/50 mg) FDC tablets Test formulation 3 (high drug loading) under fasted conditions (Test 3)
- Treatment E: Single oral dose of nirmatrelvir/ritonavir 300/100 mg (3 × 100/33.3 mg) FDC tablets Test formulation 4 under fasted conditions (Test 4)

Participants will be randomly assigned to 1 of 5 sequences as below:

Treatment Sequence	Period 1	Period 2	Period 3	Period 4
Sequence 1 (N =3)	Treatment A	Treatment B	Treatment C	Treatment D
Sequence 2 (N =3)	Treatment B	Treatment C	Treatment D	Treatment E
Sequence 3 (N =3)	Treatment C	Treatment D	Treatment E	Treatment A
Sequence 4 (N =3)	Treatment D	Treatment E	Treatment A	Treatment B
Sequence 5 (N =3)	Treatment E	Treatment A	Treatment B	Treatment C

Between each treatment, a minimum of 4 days washout is proposed to minimize any residual nirmatrelvir and ritonavir concentrations prior to start of the next treatment. Participants will be discharged on Day 4 of Period 4, following completion of all assessments.

The total planned duration of participation from the Screening visit to the last follow-up phone call, is approximately 12 weeks.

Study Intervention(s)						
Intervention Name	Nirmatrelvir	Ritonavir	Nirmatrelvir/ ritonavir	Nirmatrelvir/ ritonavir	Nirmatrelvir/ ritonavir	Nirmatrelvir/ ritonavir
Arm Name (group of participants receiving a specific treatment or no treatment)	nirmatrelvir/ ritonavir commercial tablets	nirmatrelvir/ ritonavir commercial tablets	nirmatrelvir/ ritonavir FDC tablets Test formulation 1	nirmatrelvir/ ritonavir FDC tablets Test formulation 2	nirmatrelvir/ ritonavir FDC tablets Test formulation 3	nirmatrelvir/ ritonavir FDC tablets Test formulation 4

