## Pharmacokinetic Sampling Schema

Visit Identifier	Treatment Period 1 to 4														
Study Day	Day 1												Day 2	Day 3	Day 4
Planned Hours Post Dose	0	0.5	1	1.5	2	2.5	3	4	6	8	12	16	24	48	72
PK blood sampling for nirmatrelvir and ritonavir	X	X	X	X	X	X	X	X	X	X	X	X	X	X	X
CCI			█		█		█	█		█	█				
Blood/Plasma ratio sample b					X						X				
CCI					█		█			█					

a. CCI

b. Blood sample for blood/plasma ration analysis of nirmatrelvir and ritonavir will be collected for Treatment A and B only.

c. CCI

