## 4. STUDY DESIGN

### 4.1. Overall Design

This is a Phase 1, open-label, single-dose, randomized, crossover study in healthy adult participants to estimate rBA of 4 different nirmatrelvir/ritonavir 300/100 mg FDC tablets formulations (Test formulations) compared to the nirmatrelvir/ritonavir 300/100 mg commercial tablet formulation (Reference formulation) under fasted conditions. The study will also assess the safety and tolerability, of nirmatrelvir/ritonavir FDC and commercial tablet formulations in healthy adult participants. CCI [REDACTED]

Approximately 15 healthy male and/or female participants will be enrolled and randomized to 1 of 5 possible treatment sequences to ensure at least 12 participants will complete the study. Participants who discontinue from the study for non-safety reasons may be replaced at the sponsor's discretion in collaboration with the investigator. The replacement participant will receive the same treatment sequences as the participant who discontinued.

The study will consist of 5 treatments. Each enrolled participant will participate in 4 study periods to receive 4 different treatments according to the sequence determined by randomization:

- Treatment A: Single oral dose of nirmatrelvir/ritonavir 300 (2 × 150 )/100 mg commercial tablets under fasted conditions (Reference)

- Treatment B: Single oral dose of nirmatrelvir/ritonavir 300/100 mg (2 × 150/50 mg) FDC tablets Test formulation 1 (low disintegrant) under fasted conditions (Test 1)
- Treatment C: Single oral dose of nirmatrelvir/ritonavir 300/100 mg (2 × 150/50 mg) FDC tablets Test formulation 2 (high disintegrant) under fasted conditions (Test 2)
- Treatment D: Single oral dose of nirmatrelvir/ritonavir 300/100 mg (2 × 150/50 mg) FDC tablets Test formulation 3 (high drug loading) under fasted conditions (Test 3)
- Treatment E: Single oral dose of nirmatrelvir/ritonavir 300/100 mg (3 × 100/33.3 mg) FDC tablets Test formulation 4 under fasted conditions (Test 4)

Participants will be randomly assigned to 1 of 5 sequences as shown below in Table 1. Participants will be discharged on Day 4 of Period 4, following completion of all assessments. Between each treatment, a minimum of 4 days washout is proposed to minimize any residual nirmatrelvir and ritonavir concentrations prior to start of the next treatment. The total planned duration of participation from the Screening visit to the last follow-up phone call, is approximately 12 weeks.

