**Table 1. Randomized Treatment Sequences**

Treatment Sequence	Period 1	Period 2	Period 3	Period 4
Sequence 1 (N =3)	Treatment A	Treatment B	Treatment C	Treatment D
Sequence 2 (N =3)	Treatment B	Treatment C	Treatment D	Treatment E
Sequence 3 (N =3)	Treatment C	Treatment D	Treatment E	Treatment A
Sequence 4 (N =3)	Treatment D	Treatment E	Treatment A	Treatment B
Sequence 5 (N =3)	Treatment E	Treatment A	Treatment B	Treatment C

Healthy participants will be screened to determine eligibility within 28 days prior to study treatment. Medical history and results of PEs, vital signs, 12-lead ECGs, and clinical laboratory evaluations will determine eligibility. Eligible participants will be admitted to the PCRU on Day -1 and will be confined in the PCRU until discharge on Day 4 of Period 4.

On Day 1 of each period, participants will receive a single oral dose of study intervention nirmatrelvir/ritonavir 300/100 mg as per the randomization schedule. Study treatments will be administered with approximately 240 mL of ambient temperature water under fasted conditions (overnight fast of at least 10 hours and no food until 4 hours after dosing). Serial PK samples will be collected up to 72 hours post dose. CCI

**CCI** [REDACTED]. Participants will be discharged from the PCRU on Day 4 of Period 4, following completion of all assessments.

If a participant has any clinically significant, study related abnormalities at the conclusion of a scheduled inpatient portion of the study, the Pfizer medical monitor (or designated representative) should be notified and the participant may be asked to remain in the PCRU until such abnormalities are deemed not clinically significant, or it is safe for outpatient follow-up. A safety follow-up call will be made to participants approximately 28 to 35 days from administration of the final dose of study intervention.

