## **4.2. Scientific Rationale for Study Design**

Nirmatrelvir/ritonavir FDC tablet is an alternative formulation for current commercial tablets to increase the adherence. The 4 different test formulations are designed to evaluate the effect of nirmatrelvir drug loading and disintegrant level on the performance of FDC tablets relative to the commercial product. The objective of the study is to estimate the rBA of nirmatrelvir/ritonavir of 4 different FDC tablets formulations (Test formulations) compared to the nirmatrelvir/ritonavir commercial tablets (Reference formulation) under fasted conditions. The study will also assess the safety and tolerability of nirmatrelvir/ritonavir oral FDC and commercial tablet formulations in healthy adult participants.

The study is being designed as a crossover study to account for any period effect. Between each treatment, a minimum of 4 days washout is proposed to minimize any residual nirmatrelvir and ritonavir concentrations prior to start of the next treatment, as nirmatrelvir has a half-life of approximately 6 to 13 hours when co-administered with ritonavir.

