## **10. SUPPORTING DOCUMENTATION AND OPERATIONAL CONSIDERATIONS**

### **10.1. Appendix 1: Regulatory, Ethical, and Study Oversight Considerations**

#### **10.1.1. Regulatory and Ethical Considerations**

This study will be conducted in accordance with the protocol and with the following:

- Consensus ethical principles derived from international guidelines, including the Declaration of Helsinki and CIOMS International Ethical Guidelines;
- Applicable ICH GCP guidelines;
- Applicable laws and regulations, including applicable privacy laws.

The protocol, protocol amendments, ICD, SRSD(s), and other relevant documents (eg, advertisements) must be reviewed and approved by the sponsor, submitted to an IRB/EC by the investigator, and reviewed and approved by the IRB/EC before the study is initiated.

Any amendments to the protocol will require IRB/EC approval before implementation of changes made to the study design, except for changes necessary to eliminate an immediate hazard to study participants.

Protocols and any substantial amendments to the protocol will require health authority approval prior to initiation except for changes necessary to eliminate an immediate hazard to study participants.

The investigator will be responsible for the following:

- Providing written summaries of the status of the study to the IRB/EC annually or more frequently in accordance with the requirements, policies, and procedures established by the IRB/EC;
- Notifying the IRB/EC of SAEs or other significant safety findings as required by IRB/EC procedures;
- Providing oversight of the conduct of the study at the site and adherence to requirements of 21 CFR, ICH GCP guidelines, the IRB/EC, European regulation 536/2014 for clinical studies, European Medical Device Regulation 2017/745 for clinical device research, and all other applicable local regulations.

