**Table 2. PK Parameters to be Summarized Descriptively by Analyte and Treatment**

Parameter	Summary Statistics
$AUC_{inf}$ , $AUC_{last}$ , $AUC_{12}$ , $C_{max}$ , CCI	N, arithmetic mean, median, cv%, standard deviation, minimum, maximum, geometric mean and geometric cv%.
C CI	

*For  $AUC_{inf}$  (if data permits),  $AUC_{last}$ , and  $C_{max}$ , a listing of the individual participant ratios (Test/Reference) will be provided.*

Supporting data from the estimation of **CC**  $AUC_{inf}$  or  $AUC_{last}$  will be listed by analyte and treatment: terminal phase rate constant ( $k_{el}$ ); goodness of fit statistic from the log-linear regression ( $r^2$ ); the percent of  $AUC_{inf}$  based on extrapolation ( $AUC_{extrap\%}$ ); and the first, last, and number of time points used in the estimation of  $k_{el}$ . This data may be included in the clinical study report.

Presentations for nirmatrelvir and ritonavir concentrations separately will include:

- A listing of all concentrations sorted by participant ID, period and nominal time postdose. The concentration listing will also include the actual times. Deviations from the nominal time will be given in a separate listing.
- A summary of concentrations by treatment and nominal time postdose, where the set of statistics will include n, mean, median, standard deviation, coefficient of variation (cv), minimum, maximum and the number of concentrations above the lower limit of quantification.
- Median concentrations time plots (on both linear and semi-log scales) against nominal time postdose by treatment (all treatments on the same plot per scale, based on the summary of concentrations by treatment and time postdose).
- Mean concentrations time plots (on both linear and semi-log scales) against nominal time postdose by treatment (all treatments on the same plot per scale, based on the summary of concentrations by treatment and time postdose).
- Individual concentration time plots by treatment (on both linear and semi-log scales) against actual time postdose (there will be separate spaghetti plots for each treatment per scale).
- Individual concentration time plots by participant (on both linear and semi-log scales) against actual time postdose [there will be separate plots for each participant (containing all treatments) per scale].

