## 10. APPENDICES

### Appendix 1. SAS CODE FOR ANALYSES

- An example of the PROC MIXED code is provided below:

```
proc mixed data=tab.pk;
  class seq period trt subject;
  model l&var= seq period trt / ddfm=KR;
  random subject(seq) / subject = subject(seq);
  lsmeans trt;
  estimate 'B vs A' trt -1 1 0 0 0;
  estimate 'C vs A' trt -1 0 1 0 0;
  estimate 'D vs A' trt -1 0 0 1 0;
  estimate 'E vs A' trt -1 0 0 0 1;
  ods 'Estimates' out=est&var;
  ods 'lsmeans' out=ls&var;
  ods 'covparms' out = cov&var;
  ods 'tests3'    out = tst&var;
run;
```

/\* Letter assignments for treatments (trt) within the estimate statement above are as follows;

A= Single oral dose of nirmatrelvir/ritonavir 300 (2 × 150)/100 mg commercial tablets under fasted conditions (Reference)

B = Single oral dose of nirmatrelvir/ritonavir 300/100 mg (2 × 150/50 mg) FDC tablets Test formulation 1 (low disintegrant) under fasted conditions (Test 1)

C = Single oral dose of nirmatrelvir/ritonavir 300/100 mg (2 × 150/50 mg) FDC tablets Test formulation 2 (high disintegrant) under fasted conditions (Test 2)

D = Single oral dose of nirmatrelvir/ritonavir 300/100 mg (2 × 150/50 mg) FDC tablets Test formulation 3 (high drug loading) under fasted conditions (Test 3)

E = Single oral dose of nirmatrelvir/ritonavir 300/100 mg (3 × 100/33.3 mg) FDC tablets Test formulation 4 under fasted conditions (Test 4) \*/;

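### Does the plain cyclic sequence set in Table 1 let carryover bias the Test/Reference ratios?

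*Protocol*

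**What the plan says.** Protocol 4.1 states: "Participants will be randomly assigned to 1 of 5 sequences as shown below in Table 1". Under "Table 1. Randomized Treatment Sequences" it lists five sequences with 3 participants each: ABCD, BCDE, CDEA, DEAB, EABC. The synopsis (Study Arms and Duration) and SAP 2.1 repeat them, introduced by "Participants will be randomly assigned to 1 of 5 sequences as below". Each participant receives four of the five treatments.

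The analysis model has sequence, period and treatment as fixed effects and participant within sequence as a random effect (Protocol 9.3.2, SAP 8.2). The code in SAP Appendix 1 reads "model l&var= seq period trt / ddfm=KR"; there is no carryover term.

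Against residual drug the plan relies on a washout of at least 4 days, which footnote q of the Schedule of Activities defines as the interval between doses. Protocol 4.2 supports this interval "as nirmatrelvir has a half-life of approximately 6 to 13 hours when co-administered with ritonavir". The Pharmacokinetic Sampling Schema includes a 0 h sample in Periods 1 to 4 in the row "PK blood sampling for nirmatrelvir and ritonavir". SAP 8.2 plans "A listing of all concentrations sorted by participant ID, period and nominal time postdose". It also plans a summary by treatment and nominal time that counts the values above the limit of quantification.

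**The concern.** A reader who lists the transitions in Table 1 finds 45 of them (15 participants, 3 each) on only five ordered pairs: A-B, B-C, C-D, D-E and E-A, 9 times each. After Period 1, B always follows A, C always follows B, and so on round the cycle. Predecessor and treatment are then largely confounded. Reference A always follows E, so any carryover from E reaches all four primary comparisons.

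Other cyclic sets avoid this at no cost in precision. Cycling A-B-D-C, for example, gives 15 different transitions, 3 times each. Table 1 is one of the 4 sets, among the 24 obtained by cycling one four-period sequence, with the largest maximum carryover weight. If formulation-specific carryover were material, the bioavailability ratios would be biased, and the planned model would not show it.

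**Working it through.** **1. The plan's own precision figure.** Inputs from Protocol 9.5: within-participant SD 0.1378 (nirmatrelvir lnCmax), n = 15, 90% CI, 80% coverage probability. Residual df = 60 − 15 − 3 − 4 = 38.

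Half-width = t(0.95, 38) × SD × √(2/15) × √(χ²(0.80, 38)/38) = 1.686 × 0.1378 × 0.3651 × √(45.08/38) = 0.0924, as stated. The same formula gives the other three stated values: 0.1175, 0.1625 and 0.2201.

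**2. How carryover enters.** I set up the 60 observations with participant, period and treatment effects and projected an indicator for the preceding treatment onto each T − A contrast. Weights on the carryover of each formulation:

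| Contrast | A | B | C | D | E |
|---|---|---|---|---|---|
| B/A | 0.800 | −0.067 | 0 | 0 | −0.733 |
| C/A | 0.067 | 0.733 | −0.067 | 0 | −0.733 |
| D/A | 0.067 | 0 | 0.733 | −0.067 | −0.733 |
| E/A | 0.067 | 0 | 0 | 0.733 | −0.800 |

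Every row sums to zero, so carryover shared by all formulations drops out. The positive weights in each row sum to 0.80, so the bias is at most 0.80 times the spread in carryover between formulations.

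**3. How large the spread can be.** Inputs: 96 h between doses (minimum) and a nirmatrelvir half-life of 6 to 13 h. The residual fraction is taken as the carryover on the log scale.

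- 13 h: 0.5^(96/13) = 0.00598, or 0.6%.
- 6 h: 0.5^(96/6) = 0.000015, or about 0.002%.

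**4. Bias limits at 13 h.**

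- Some formulations leave the full 0.6%, others nothing: 0.80 × 0.00598 = 0.0048.
- Residues proportional to bioavailabilities of 0.8 to 1.25 (assumption, spread 0.45): 0.80 × 0.45 × 0.00598 = 0.0022.

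Against the smallest half-width these are 0.0048/0.0924 = 5.2% and 0.0022/0.0924, about 2%. Against the nirmatrelvir AUCinf half-width the first is 0.0048/0.1175 = 4.1%.

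Under Table 1, Var(T − A) = 0.1778 × SD². With SD 0.1378 this is 0.00338, so SE = 0.058. The extreme bias adds 0.0048²/0.00338 = 0.7% to the mean squared error.

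**5. What other sequences would gain.** For the A-B-D-C cycle, Var(T − A) is also 0.1778 × SD². The largest weight falls to 0.33, and the positive weights sum to 0.60 (B/A, E/A) or 0.333 (C/A, D/A). The extreme limits become 0.60 × 0.00598 = 0.0036 and 0.333 × 0.00598 = 0.0020. The gain is at most 0.0048 − 0.0020 = 0.0028 on the log scale.

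**6. Would a carryover fit help?** With four carryover terms, Var(T − A) rises to 0.92–0.96 × SD² under Table 1 and 0.21–0.25 × SD² under the alternative. Even in the alternative, a difference between two carryover effects has variance 0.29–0.39 × SD². At SD 0.1378 its SE is about 0.075 to 0.086, or 12 to 14 times the 0.006 it would be looking for.

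**7. Ritonavir.** The visible text gives no half-life, so I ask what value would matter. For the extreme limit to reach a tenth of the ritonavir AUCinf half-width (0.01625), the spread must be 0.01625/0.80 = 0.0203. That corresponds to 5.62 half-lives in 96 h, so a half-life of 96/5.62 = 17.1 h, again with some formulations leaving nothing.

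**The case for a change.** The strongest counter-argument is that the washout calculation covers residual nirmatrelvir only. Ritonavir is given to inhibit CYP3A4, and inhibition that outlasted measurable drug would not show in a predose sample. The test formulations differ deliberately in drug load and disintegrant. Since a set with varied predecessors has exactly the same variance, it would be free insurance if adopted before the randomisation list is used.

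The algebra behind this stands, and so does the equal variance. The rest does not carry the point:

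- Only a difference between formulations matters. All five treatments deliver the same 300/100 mg, and nothing in the visible text says that inhibition outlasts measurable ritonavir or differs by formulation at 96 h. Protocol 6.9 itself ends its restriction on medicines highly dependent on CYP3A4 at 4 days after the last dose, the same interval as the minimum washout.
- PK summaries are partly redacted and further detail is referred to the Investigator's Brochure. The missing ritonavir half-life therefore cannot be counted as an omission.
- Residual drug of either analyte would be seen. Each treatment is given to 12 participants, 3 of them in Period 1, so 9 of its 12 predose samples follow its one predecessor. The planned 0 h summary by treatment is thus already a summary by preceding treatment, apart from Period 1. A separate table would add almost nothing.
- The change is not free in practice. It alters the study design, and under Protocol 10.1.1 "Any amendments to the protocol will require IRB/EC approval before implementation of changes made to the study design". It would also need a new randomisation list and a SAP edit, and it gains nothing once the list is in use.

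**Conclusion.** The concern does not hold. Table 1 does give each treatment a single predecessor, with weights of 0.73 to 0.80 on differential carryover. It is nevertheless a sound design: each treatment occurs once per period across the five sequences, and treatment pairs are balanced within participants. The documents never claim balance for predecessors, and no stated figure or rule is wrong. The study estimates ratios without hypotheses or decision rules (Protocol 9.1, SAP 4).

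On the plan's own half-life and washout, the bias from residual nirmatrelvir is at most 0.0048 on the log scale in an implausible extreme, and at most 0.0022 on the milder assumption. The smallest planned half-width is 0.0924. No reported ratio or interval would read differently under another sequence set.

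This rests on a gap of at least 96 h, a half-life of no more than 13 h, first-order elimination, and residual drug as the route of carryover. For ritonavir it rests on the predose samples, because no half-life is visible. Preferring one sequence set to another of equal variance is a matter of taste here.

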**Table 1. Randomized Treatment Sequences**

Treatment Sequence	Period 1	Period 2	Period 3	Period 4
Sequence 1 (N =3)	Treatment A	Treatment B	Treatment C	Treatment D
Sequence 2 (N =3)	Treatment B	Treatment C	Treatment D	Treatment E
Sequence 3 (N =3)	Treatment C	Treatment D	Treatment E	Treatment A
Sequence 4 (N =3)	Treatment D	Treatment E	Treatment A	Treatment B
Sequence 5 (N =3)	Treatment E	Treatment A	Treatment B	Treatment C

Healthy participants will be screened to determine eligibility within 28 days prior to study treatment. Medical history and results of PEs, vital signs, 12-lead ECGs, and clinical laboratory evaluations will determine eligibility. Eligible participants will be admitted to the PCRU on Day -1 and will be confined in the PCRU until discharge on Day 4 of Period 4.

On Day 1 of each period, participants will receive a single oral dose of study intervention nirmatrelvir/ritonavir 300/100 mg as per the randomization schedule. Study treatments will be administered with approximately 240 mL of ambient temperature water under fasted conditions (overnight fast of at least 10 hours and no food until 4 hours after dosing). Serial PK samples will be collected up to 72 hours post dose. CCI

**CCI** [REDACTED]. Participants will be discharged from the PCRU on Day 4 of Period 4, following completion of all assessments.

If a participant has any clinically significant, study related abnormalities at the conclusion of a scheduled inpatient portion of the study, the Pfizer medical monitor (or designated representative) should be notified and the participant may be asked to remain in the PCRU until such abnormalities are deemed not clinically significant, or it is safe for outpatient follow-up. A safety follow-up call will be made to participants approximately 28 to 35 days from administration of the final dose of study intervention.

